Nintedanib is hypothesized to have the same relative effect on all patients with PF-ILD (an approximate 50% reduction in the annual rate of decline in FVC). However it is expected that the absolute effect difference between groups will be the largest in the patients with HRCT with UIP-like fibrotic pattern only since these patients are assumed to have a larger annual rate of decline than patients with other HRCT fibrotic patterns.

The treatment effect to detect is therefore in the range of 75-100 mL/year for the PF-ILD patients with HRCT with UIP-like fibrotic pattern only and of 60-75 mL/year in the PF-ILD patients with other HRCT fibrotic patterns.

Given some expected heterogeneity in the rate of decline across the PF-ILD subpopulations, the variability is assumed to be larger than in IPF for patients with other HRCT fibrotic patterns with a standard deviation (SD) of 400 mL/year. For patients with HRCT with UIP-like fibrotic pattern only, a more homogeneous group of patients, the variability is assumed to be the same as observed in IPF with a SD of 300 mL/year.

By enrichment, it is planned to recruit 400 PF-ILD patients with HRCT with UIP-like fibrotic pattern only, making up two thirds (66.7%) of the study population. This design will be used in order to maintain a high power to detect a clinically meaningful effect of nintedanib in the rare disease of PF-ILD.

There will be two co-primary analysis populations: the first will comprise all patients (the overall population); the second will comprise all patients with HRCT with UIP-like fibrotic pattern only. Since establishing an effect in either of these two populations is considered clinically relevant, the trial will be considered positive if it establishes efficacy in either one of the two populations or in both.

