In order to maintain an overall type 1 error rate of 5%, a Hochberg procedure will be used ([R97-1003](#)). This multiplicity adjustment strongly controls the overall Type I error rate in clinical trials with a targeted subpopulation ([R16-1041](#)). For the primary endpoint, statistical significance will be declared if the analyses in both co-primary populations are significant at the two-sided 5% level, **or** if the analyses in either co-primary population are statistically significant at the two-sided 2.5% level. Given the proposed design properties it is calculated that applying this procedure, the overall alpha spent will be 4.35% so the overall Type I error control is below 5%. This is based upon the summation of the probabilities of rejecting H_0 under various combinations of results for the co-primary populations within the Hochberg procedure (calculated using SAS® Version 9.4, see [Appendix 10.6](#) for details).

[Table 7.7: 1](#) below presents the power properties of this study for several scenarios for the treatment effect in the two co-primary populations.

Table 7.7: 1: Power properties for several scenarios for the treatment effect in the two co-primary populations

	Patients with HRCT with UIP- like fibrotic pattern only Co-primary	Patients with other HRCT fibrotic patterns	Overall patient population Co-primary	
Scenario 1				
Assumed treatment difference in absolute change in FVC in mL/year (SD)	100 (300)	75 (400)	92 (337)	
Individual test power	90.2%		90.3%	
Overall Power [*]				92.6%
Scenario 2				
Assumed treatment difference in absolute change in FVC in mL/year (SD)	75 (300)	60 (400)	70 (337)	
Individual test power	67.2%		68.2%	
Overall Power [*]				72.4%
Scenario 3				
Assumed treatment difference in absolute change in FVC in mL/year (SD)	75 (300)	75 (400)	75 (337)	
Individual test power	68.2%		73.4%	
Overall Power [*]				75.8%

FVC, forced vital capacity; SD, standard deviation.

Power calculations are based on Hochberg procedure at the overall type 1 error rate of 5% (two-sided), with 200 patients with HRCT with UIP-like fibrotic pattern only and 100 patients with other HRCT fibrotic patterns per treatment group.

*The overall power is the probability of concluding statistical significance for either of the co-primary populations.

Power calculated using SAS[®] Version 9.4 (see [Appendix 10.6](#) for details)

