4.3 CLARIFICATIONS

The following points warrant further clarification:

- Within this document, "drug intake" refers to the intake of the trial medication – either placebo or nintedanib.

- This study comprises of the following “populations”: The “overall” population and the subpopulation of patients with “HRCT with UIP-like fibrotic pattern only” are considered to be co-primary populations. The subpopulation of patients with “other HRCT fibrotic patterns” is considered to be the complementary population. Unless stated otherwise in the TSAP, evaluations are only done for the co-primary populations.
- In order to determine whether the results for the primary endpoint are consistent between the subpopulation of patients with “HRCT with UIP-like fibrotic pattern only” and the subpopulation of patients with “other HRCT fibrotic patterns” the following steps will be taken
 - The numerical results, including the 95% CI will be inspected visually
 - HRCT pattern will be treated as a subgroup in one sensitivity analysis, and the obtained interaction p-value will be depicted on a forest plot in addition to the results of the “overall” population, the subpopulation of patients with “HRCT with UIP-like fibrotic pattern only” and the subpopulation of patients with “other HRCT fibrotic patterns”. See [Section 7.4.3](#) for additional details.
- Due to the possible occurrence of mis-stratifications during the randomisation process, the HRCT pattern as reported in the eCRF will be used in all analyses. In case this occurs in more than 3% of all randomised patients, an additional sensitivity analysis is implemented utilising the values used during the randomisation process in the Interactive Response Technology (IRT) system. See [Section 7.4.2.2.2](#) for additional details.
- Two patients were randomised by mistake, whose disease extent was $\leq 10\%$ and whose HRCT pattern was not determined by the central readers. Both patients were randomised under “other HRCT fibrotic patterns”. Given that the HRCT pattern was actually not determined, those patients do not have an entry for this variable in the eCRF. They will be counted in the subpopulation of patients with “other HRCT fibrotic patterns” in all analyses within the CTR except for the sensitivity analysis implemented to evaluate the mis-stratifications – there they will be counted in the subpopulation of patients with “HRCT with UIP-like fibrotic pattern only”. See [Section 6.6](#) for further details.

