7. PLANNED ANALYSIS

Planned analyses can be categorized based on:

- The study period for which they are performed:
 - Over 52 weeks (Part A) and over the whole trial (Part A and Part B together)
- The study population for which they are performed:
 - The co-primary populations (“overall” population or sub-population of patients with “HRCT with UIP-like fibrotic pattern only”), or the complementary patient population of patients with “other HRCT fibrotic patterns”.

Unless specified otherwise, analyses over 52 weeks (Part A) and over the whole trial (Part A and Part B) will be produced on both co-primary populations. In addition, selected analyses over 52 weeks and over the whole trial will be produced on the complementary population of patients with “other HRCT fibrotic patterns”. Details can be found in subsequent sections. Please note that analyses based on the complementary population will, by default with only few exceptions, be part of the CTR appendix.

The labelling and display format of statistical parameters will follow BI standards (9). For End-Of-Text tables, the set of summary statistics is: N / Mean / SD / Min / Median / Max. In descriptive statistics tables, mean, sd and median will be rounded to one additional digit than the raw individual value. In case extreme data outside of the expected range are observed, quartiles and percentiles will be presented additionally.

Tabulations of frequencies for categorical data will include all categories depicted in the eCRF and will display the number of observations in a category as well as the percentage (%) relative to the respective treatment group (unless otherwise specified, all patients in the respective patient set whether they have non-missing values or not). Percentages will be rounded to one decimal place. The category missing will be displayed only if there are actually missing values.

If not otherwise specified, two-sided p-values and confidence intervals will be displayed. Please note that the depiction of p-values in outputs will be limited to the following evaluations:

- Primary analysis performed in both co-primary populations
- Sensitivity analyses of the primary endpoint analysis in both co-primary populations
- Nominal p-values for the evaluation of the main secondary endpoints, evaluated in both co-primary populations
- Interaction p-values for the efficacy evaluations in the subgroup analyses

The primary analyses will include all treated patients.

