7.4.3 Subgroup analyses

For each subgroup analysis (refer to [Section 6.4](#) for an overview of subgroups) of the primary endpoint, the heterogeneity of the subgroup treatment effect on the slope will be estimated: A random slope and intercept mixed model will be fitted based upon the statistical model for the primary analysis but parametrised using the treatment-by-subgroup and the treatment-by-subgroup-by-time interaction terms. A contrast statement, with appropriate contrasts, will be used to conduct an F-test of heterogeneity across all expression levels of the subgrouping. The results will be discussed and may be explored further.

It can be shown that the following simplified, saturated model is equivalent to the fully specified model and will therefore be used for the analysis of subgroups:

$$y_{ijkmu} = (\alpha + a_i + \vartheta_m + \beta_0 S_i + \delta_{ku}) + (\gamma + g_i + \beta_s S_i + \theta_{ku}) t_{ij} + e_{ij}$$

$$(a_i, g_i) \sim N_2 (\mathbf{0}, \Sigma)$$

$$e_{ij} \stackrel{iid}{\sim} N (0, \sigma^2)$$

The components of the model are identical to the primary model (see [Section 7.4.1](#) for explanation of notions) only adding the subgroup covariate:

δ_{ku} = intercept coefficient for the effect of treatment k in subgroup category u for patient i

θ_{ku} = slope coefficient for the effect of treatment k in subgroup category u for patient i

Please note: For the subgroups where the co-primary population is also evaluated, the term for HRCT pattern will be excluded from the model. In addition, evaluations are also only reasonable if enough subjects are present within the subgroup – for this evaluation there need to be at least 5 observations per treatment per subgroup expression level per visit. If this is not given, it is possible to pool similar subgroup expression levels together. Whether subgroup expression levels can and should be pooled will be decided at the final Blinded Report Planning Meeting (BRPM) and documented in the minutes. Section 9.8 of the CTR will then also discuss the pooling of subgroup expression levels and provide a medical rationale.

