In addition to the subgroup evaluations described above, one output will be computed treating the HRCT pattern and its expression levels (“HRCT with UIP-like fibrotic pattern only” / “other HRCT fibrotic patterns”) as subgroups. The model would exclude the term for the HRCT pattern, and the obtained interaction p-value would serve as objective measurement whether the results of the primary endpoint are consistent between the subpopulation of patients with “HRCT with UIP-like fibrotic pattern only” and the subpopulation of patients with “other HRCT fibrotic patterns”.

Table 7.4.3: 1 Subgroup analyses – List of analyses

Description of study population	
 Disposition of patients Demographic data Trial indication characteristics Baseline pulmonary efficacy variables Baseline conditions Exposure to study drug over 52 weeks Exposure to actual treatment dose received over 52 weeks
Efficacy analyses on the primary endpoint in the overall population [1]	
 Forest-plot for rate of decline in FVC (ml/yr) over 52 weeks in all subgroups: representation on the same graph of the estimate, 95% Confidence Interval and p-value of F-test for heterogeneity across all levels of the subgrouping. Rate of decline in FVC (ml/yr) over 52 weeks by subgroup Graphical representation of the mean (SEM) observed FVC change from baseline (ml) over time by subgroup over 52 weeks Graphical representation of the mean (SEM) estimated FVC change from baseline (ml) over time by subgroup over 52 weeks
Safety analyses in the overall population [1][2]	
 Adverse event overall summary over 52 weeks Frequency of patients with adverse events by SOC and PT over 52 weeks Frequency of patients with adverse events occurring with incidence in preferred term > 5% in at least one treatment arm by SOC and PT over 52 weeks Frequency of patients with serious adverse events by SOC and PT over 52 weeks Frequency of patients with investigator defined related adverse events by SOC and PT over 52 weeks Frequency of patients with adverse events leading to treatment discontinuation events by SOC and PT over 52 weeks Frequency of patients with adverse events leading to death by SOC and PT over 52 weeks Frequency of patients with adverse events by safety topic over 52 weeks Frequency of patients with serious adverse events by safety topic over 52 weeks

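### The HRCT-pattern interaction p-value cannot serve as the objective measure of consistency: it would usually be non-significant at 5% even if other-pattern patients had no benefit

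*SAP*

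**What the plan says.** SAP 4.3 lists two steps for deciding whether the primary result is consistent between the UIP-like subpopulation and the other-pattern subpopulation. First: "The numerical results, including the 95% CI will be inspected visually". Second: "HRCT pattern will be treated as a subgroup in one sensitivity analysis, and the obtained interaction p-value will be depicted on a forest plot", next to the results for the overall population and the two subpopulations. SAP 7.4.3 then gives the second step a specific property: "the obtained interaction p-value would serve as objective measurement" of whether the primary endpoint results agree between the two subpopulations.

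For subgroup analyses in general, SAP 7.4.3 says a contrast "will be used to conduct an F-test of heterogeneity across all expression levels of the subgrouping". None of these places gives a significance level for the test, a size of difference that would count as inconsistent, or the scale on which consistency is meant. SAP 4.3 does say that the trial is sized only for the primary endpoint analysis.

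Two other places bear on the point. SAP 7.4.1 fits the primary model in other-pattern patients but shows no p-value for it. The example code in SAP 9.5.2 estimates slopes and the treatment difference within each subgroup level. The comparison between levels appears only as a CONTRAST, which returns a test and no estimate or CI.

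**The concern.** A p-value from a test of no interaction can measure consistency only if it would probably be small when the effects truly differ by an amount that matters. With one third of the trial in the other-pattern stratum, and the larger SD assumed there, that has to be checked.

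The stake is what the report may say about other-pattern patients. They belong to the overall co-primary population, and no p-value is shown for them alone. The interaction p-value is therefore the only displayed test result on whether they share the effect seen in UIP-like patients. If it is non-significant and carries the label the SAP gives it, a reader will take it as agreement. The quantity that would show how imprecise the comparison is, the estimated difference with its interval, is not planned.

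The measure can also mislead in the other direction. The test compares absolute slopes in mL/year, while Protocol 7.7 assumes about the same 50% relative reduction in all patients and expects a larger absolute effect in the UIP-like group. A significant interaction could be compatible with the plan's own idea of a consistent effect.

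**Working it through.** **Inputs.** From Protocol 7.7: SD 300 mL/year (UIP-like) and 400 mL/year (other), 200 and 100 patients per treatment group, no allowance for drop-out. "The treatment effect to detect is therefore in the range of 75-100 mL/year" for UIP-like patients, and 60 to 75 for the others. From Protocol 7.6: 1:1 allocation within stratum. From SAP 7: "If not otherwise specified, two-sided p-values and confidence intervals will be displayed". The level for the interaction test is not stated; 5% is assumed, with 10% and 20% also shown.

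**Reproducing the plan's figures.** The documents give no power for the interaction, so the check is on Protocol Table 7.7: 1, using the Appendix 10.6 method: bivariate normal statistics with correlation √0.667, tested at two-sided 5% and 2.5%. The standard errors are 337·√(2/300) = 27.5 (overall) and 300·√(2/200) = 30.0 (UIP-like).

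| Scenario | Recomputed UIP-like / overall population / overall power | Table 7.7: 1 |
|---|---|---|
| 1 | 90.2 / 90.3 / 92.6% | same |
| 2 | 67.2 / 68.2 / 72.4% | same |
| 3 | 68.2 / 73.4 / 75.8% | same |

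The two-sided type I error also matches (Protocol 7.7, in percent: "the overall alpha spent will be 4.35"). The inputs are therefore being used as the protocol uses them.

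**Standard error of the interaction.** The strata are disjoint, so the variances add:

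- UIP-like: 300·√(2/200) = 30.0
- Other: 400·√(2/100) = 56.6
- Difference: √(30.0² + 56.6²) = 64.0 mL/year
- 95% CI half-width: 1.96 × 64.0 ≈ 126 mL/year
- Difference detectable with 80% power at 5%: 2.80 × 64.0 ≈ 179 mL/year

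**Power.** With d the true difference, power = Φ(d/64.0 − z) + Φ(−d/64.0 − z). For d = 100 at 5%: 100/64.0 = 1.56, less 1.96 is −0.40, giving 34.5%. For d = 75: 1.17 − 1.96 = −0.79, giving 21.6%.

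| True effects, UIP-like vs other (mL/year) | d | 5% level | 10% level | 20% level |
|---|---|---|---|---|
| 100 vs 0 | 100 | 34.5% | 46.8% | 61.3% |
| 75 vs 0 | 75 | 21.6% | 32.0% | 46.3% |
| 100 vs 75 (Scenario 1) | 25 | 6.8% | 12.6% | 23.4% |
| 75 vs 60 (Scenario 2) | 15 | 5.6% | 10.9% | 21.2% |
| 75 vs 75 (Scenario 3) | 0 | 5.0% | 10.0% | 20.0% |

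The first two rows are the informative ones. The differences in Scenarios 1 and 2 are what a common 50% reduction gives: half of 200 and 150 is 100 and 75, and half of 150 and 120 is 75 and 60. Scenario 3 has no difference, so its row is only the type I error.

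**Variants at 5%.** With SD 300 in both strata the standard error is 52.0, and power is 48.6% (100 vs 0) and 30.3% (75 vs 0). If the single covariance structure in the SAP model pools the two SDs, the model standard error is about 58 against a true 64. The rejection rates are then 41.2% and 27.1%, with 7.4% when there is no difference. All remain below one half.

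**The case against.** The strongest reply is that the SAP does not rely on this p-value alone. SAP 4.3 puts visual inspection first, and Protocol 7.3.1 already plans a forest plot of the three effects with 95% CIs. SAP 7.4.3 says that subgroup results will be discussed and perhaps explored further, and SAP 4.3 says that only the primary analysis is powered. A reader could also combine the two displayed intervals: half-widths of about 59 and 111 give √(59² + 111²) ≈ 126. Finally, a CI that wide cannot prove consistency either, and low interaction power is normal in a trial of this size. All of this stands. It limits the point to the role given to the p-value and to the missing difference estimate; it does not justify the word objective.

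Three stronger readings are tempting, and the documents do not support them.

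- *That the SAP has a rule under which a non-significant interaction is declared consistent.* It states no threshold and no such rule; the 5% level here is an assumption.
- *That the test is useless because its power is about 7%.* That is Scenario 1, a difference the plan itself expects under equal relative effects, so failing to flag it is no defect.
- *That the overall-population claim depends on this test.* Success is defined by the Hochberg procedure on the two co-primary populations. The interaction belongs to a sensitivity analysis and gates nothing.

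**Conclusion.** The point holds as a fault of interpretation and reporting. On the protocol's planning values the interaction p-value does not have the property that SAP 7.4.3 assigns to it. At two-sided 5%, it would miss a complete absence of benefit in other-pattern patients about 65% of the time if the UIP-like effect is 100 mL/year, and about 78% of the time if it is 75. At a 20% level the miss rates are about 39% and 54%. If the estimated difference were exactly zero, its 95% CI would run from about −126 to +126 mL/year, wider than any treatment effect the plan assumes.

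This rests on the planned SDs and stratum sizes, no drop-out, a normal approximation to the slope comparison, and the assumed level. The variants above do not change it. Primary test, type I error and sample size need no change.

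**What to change.** - In SAP 7.4.3, replace the sentence that calls the p-value an objective measurement, and align the consistency bullet in SAP 4.3. Say that the p-value is descriptive and that a non-significant interaction does not establish consistency.
- Add an ESTIMATE, with confidence limits, for the between-pattern difference in treatment effect on slope. In the SAP 9.5.2 layout it can reuse the four coefficients of the CONTRAST statement, with the sign checked against the order of the HRCT levels. Print it with its 95% CI on the planned forest plot, and state in advance that the expected half-width is about 126 mL/year.
- State whether consistency is judged on the absolute scale (mL/year) or relative to the placebo decline. If absolute, acknowledge that equal relative effects imply a non-zero difference (15 to 25 mL/year in Scenarios 1 and 2).

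The cost is one ESTIMATE statement, one more line on an existing figure and a short wording change. No new data or patients are needed.

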7.5 SECONDARY ENDPOINTS

Please note that any p-values presented for secondary endpoints will be considered nominal in nature and no adjustment for multiplicity will be made.

7.5.1 Key secondary endpoints

This section is not applicable as no key secondary endpoint has been specified in the protocol.

7.5.2 Secondary endpoints

All secondary endpoints are defined over the 52 weeks period only.

7.5.2.1 Main secondary efficacy endpoints

7.5.2.1.1 King's Brief Interstitial Lung Disease Questionnaire (K-BILD) Total Score

The absolute change from baseline in K-BILD total score between week 52 and baseline will be presented graphically as well as numerically to illustrate the impact of the underlying condition on the patient's health status. The descriptive analyses of the absolute change from baseline in K-BILD total score will also be shown for the complementary population.

All sub-domain scores (breathlessness and activities, psychological, chest symptoms) will also be presented for all time points separately, as well as change from baseline.

In addition to the descriptive evaluation, absolute change from baseline in K-BILD total score between week 52 and baseline will also be analysed in the TS using a restricted maximum likelihood (REML) based repeated measures approach. An unstructured variance-covariance structure will be used to model the within patient measurements. In the event of non-convergence, the same methods used in the primary analyses ([Section 7.4.1](#)) will be implemented to overcome the issue. The HRCT pattern will be included as a covariate (with exception when the analysis is run in the co-primary population of patients with "HRCT with UIP-like fibrotic pattern only") as well as the baseline K-BILD total score.

A graph of the mean K-BILD total score absolute change from baseline (\pm SEM) over time for each treatment group will be displayed. The same graph will be performed on adjusted mean changes from baseline.

